7.2.3. Fedratinib Dose Adjustment for Renal Impairment

No modification of the starting dose is recommended for patients with mild to moderate renal impairment. Due to potential increase of fedratinib exposure, patients with pre-existing moderate renal impairment require more intensive safety monitoring, and if necessary, dose modifications based on adverse reactions.

In subjects that develop severe renal impairment during the study the fedratinib dose should be adjusted by 2 dose decrement levels (eg, from 400 mg to 200 mg once a day [QD]).

Clinical signs and symptoms for efficacy and fedratinib-related AEs should be monitored and the dose of fedratinib should be further adjusted as necessary.

7.2.4. Overdose

Overdose, as defined in this protocol, refers to fedratinib dosing only. On a per dose basis, an overdose is defined as any amount over the protocol-specified dose of fedratinib, regardless of any associated adverse events or sequelae.

On a schedule or frequency basis, an overdose is defined as anything more frequent than the protocol required schedule or frequency. Complete data about drug administration, including any overdose, regardless of whether the overdose was accidental or intentional, should be reported in the case report form. See Section [10.1](#) for the reporting of adverse events associated with overdose.

7.3. Overview on Management of Gastrointestinal Adverse Events (Fedratinib)

Gastrointestinal adverse events, specifically nausea, vomiting and diarrhea, are commonly associated with fedratinib treatment and require multifaceted management using dose adjustment, active treatment or prophylaxis with anti-emetics, and monitoring. GI symptoms generally start in the first treatment cycle but typically improve within 6 to 8 weeks on fedratinib treatment.

7.3.1. Management of Nausea and Vomiting

Management of nausea and vomiting during treatment with fedratinib will be done according to the following steps:

- Subjects will be provided management instructions (including when to contact the study site) before the start of treatment
- In order to mitigate for nausea and vomiting events, it is recommended to take fedratinib with food during an evening meal.
- It is highly recommended to use anti-nausea/vomiting treatment prophylactically according to local practice for the first 8 weeks of treatment (eg, ondansetron). If dimenhydrinate or other muscarinic receptor antagonists are used for nausea and vomiting, administer these agents in the evening to minimize drowsiness and other potential neurological AEs
- Hold / reduce the dose of fedratinib according to [Table 4](#)
- Hospitalization may be indicated for Grade 3 or higher nausea or vomiting or events that persist
- For medications that are administered for prophylactic use of nausea and vomiting, if no clinically significant nausea and vomiting occurs during the first 8 weeks of fedratinib treatment, consider weaning the subject off these medications

7.3.2. Management of Diarrhea

Management of diarrhea during treatment with fedratinib will be done according to the following steps:

- Subjects should have loperamide available at home and should be provided with diarrhea management instructions (including when to contact the study site) before the start of treatment
- Loperamide should not be given as prevention in case the subject does not experience diarrhea
- Treat with loperamide as per local practice at the onset of diarrhea. Consider starting loperamide at a 4 mg loading dose and then 2 mg after each diarrheal bowel movement without exceeding 16 mg/24 hours
- Dietary modifications including adequate hydration, avoidance of lactose containing foods and alcohol, small meals with rice, bananas, bread, etc
- Hold / reduce the dose of fedratinib according to [Table 4](#)
- Hospitalization may be indicated for Grade 3 or higher persisting diarrhea.
- Management of nausea, vomiting and diarrhea will be assessed during the subject's visit in the study on Day 1 of every following 28-day cycle, at Day 15 of the first 3 cycles and by a mandatory telephone contact at Day 8 of the first cycle.

7.4. Management of Encephalopathy, including Wernicke's

A potential case of encephalopathy including Wernicke's is a medical emergency. Screening for encephalopathy, including Wernicke's and management of potential cases during treatment with fedratinib will be done according the following steps:

7.4.1. Clinical and Cognitive Assessment

Interval history: including a review of the subject's history for confusion, memory problems, vision problems (eg, double vision) as well as poor nutrition, signs and symptoms of malabsorption, and alcohol use

- Physical examination: including assessment for abnormal eye movements, cerebellar abnormalities and body weight (weight loss compared to previous examination or subject history) during screening and Day 1 of every treatment cycle, at the End of Treatment (EOT), and the 30-Day Follow-up visit during the study.
- Mini-Mental State Examination (MMSE): to objectively assess for signs/symptoms of encephalopathy during screening, on Day 1 of Cycles 2 and 3 and every third cycle thereafter, and at the EOT visit for the study.

7.4.2. Management of Encephalopathy Including Wernicke's

In case of signs or symptoms that may indicate encephalopathy including Wernicke's:

- Hold fedratinib until Encephalopathy, including WE is ruled out
- Obtain sample for thiamine level
- Start parenteral thiamine supplementation, as described in Section 7.4.3 for subjects with thiamine levels < 30 nM/L regardless of thiamine level
- Report the event as an AESI to the Sponsor
- Obtain a neurological consult
- Perform a brain MRI
- If WE is confirmed, discontinue fedratinib permanently
- If WE is ruled out, assess for other causes of encephalopathy and treat accordingly. Once resolved, consider restarting treatment with fedratinib after discussion with Medical Monitor.

7.4.3. Thiamine Supplementation, Monitoring, and Correction

All subjects receiving study medication will receive thiamine supplementation. Start oral thiamine supplementation at a minimum daily dose of 100 mg (or equivalent) at Cycle 1 Day 1. Continue supplementation throughout the Treatment Period until study medication is discontinued, and through the 30-Day Follow-up visits.

Thiamine levels (for whole blood) will be monitored in all subjects.

- Thiamine levels are assessed at screening and need to be corrected and retested before starting fedratinib treatment (see inclusion criteria)

- While on treatment with study medication, thiamine levels are assessed in a fasting state at start of Cycles 1, 2, 3 and every third cycle thereafter, at the End of Treatment Visit and as clinically indicated
- In case of documented thiamine deficiency and a subject is receiving thiamine supplementation, while on study:
 - Thiamine levels should be assessed in a fasting state and thiamine supplementation should be given after the blood draw
 - If the subject develops signs or symptoms suggestive of encephalopathy including Wernicke's, please follow instruction in Section [7.4.2](#)
 - For thiamine levels below normal range but > 30 nM/L without signs or symptoms of WE while receiving thiamine supplementation:
 - The site should contact the Medical Monitor regarding the low thiamine level as soon as possible
 - Report the event as an Adverse Event of Special Interest (AESI) to the Sponsor.
 - Consider increasing the dose of oral thiamine supplementation to twice the daily dose (if the subject is taking 100 mg, increase to 200 mg)
 - Monitor thiamine level closely (monthly at least) and adjust dose as needed
 - For thiamine level < 30 nM/L **without signs or symptoms** of WE while receiving thiamine supplementation:
 - The site should contact the Medical Monitor regarding the low thiamine level as soon as possible
 - Report the event as an Adverse Event of Special Interest (AESI) to the Sponsor.
 - Study medication must be held until thiamine levels are restored to normal range.
 - Immediate treatment with IV thiamine (stop oral thiamine), at therapeutic dosages eg, 500 mg IV infused over 30 minutes 3 times daily for 2 to 3 days or alternatively IM in equivalent doses according to local standard of care
 - This will be followed by 250 mg to 500 mg IV thiamine infused once a day for 3 to 5 days or alternatively IM in equivalent doses according to local standard of care
 - And then consider increasing the dose of oral thiamine supplementation to twice the previous daily dose (for example if the subject is taking 100 mg, increase the dose to 200 mg)
 - Monitor thiamine levels closely (at least monthly) and adjust the dose as needed
 - Thiamine supplementation should be administered as a thiamine only formulation.

- If thiamine levels are low, ensure that magnesium levels are normal or corrected if low

7.5. Method of Treatment Assignment

The treatment assignment will occur at the end of the Screening Period, once all the required screening procedures have been completed, the investigator has verified the subject meets all eligibility criteria, and all required data have been submitted to the Sponsor or its authorized representative. Upon receiving acknowledgment of subject's eligibility review from the Sponsor or its authorized representative, the subject can be assigned fedratinib treatment using an IRT built for this study.

Designated research personnel at each investigational site will be assigned unique, password-protected user accounts which give them the authorization to utilize the IRT to enroll subjects.

7.6. Packaging and Labeling

The label(s) for fedratinib will include Sponsor name, address and telephone number, the protocol number, fedratinib, dosage form and strength (where applicable), amount of fedratinib per container, lot number, expiry date (where applicable), medication identification/kit number, dosing instructions, storage conditions, and required caution statements and/or regulatory statements as applicable. Additional information may be included on the label as applicable per local regulations.

7.7. Investigational Product Accountability and Disposal

Sponsor (or designee) will review with the Investigator and relevant site personnel the process for investigational product return, disposal, and/or destruction including responsibilities for the site versus Sponsor (or designee).

7.8. Investigational Product Compliance

Subjects will self-administer all fedratinib doses in the treatment phase. Study site personnel will review the dosing information with the subject (or legally authorized representative) on scheduled clinic visit days. Subjects (or legally authorized representative) will be asked to bring all unused capsules with them to scheduled clinic visits (ie, prior to the start of the next treatment Cycle). Study site personnel will perform a fedratinib administration compliance check and record this information in the subject's source documentation.

Administration of all fedratinib will be recorded including dispensing, dosing and any changes in dosage administration such as interruption or reduction in dosing due to an AE.

8. CONCOMITANT MEDICATIONS AND PROCEDURES

Over the course of this study, additional medications may be required to manage aspects of the disease state of the subjects, including side effects from trial treatments or disease progression. Supportive care, such as anti-emetic medications, may be administered at the discretion of the Investigator.

All prior/concomitant medications including, prescription, over-the-counter, and herbal preparations taken for any indication used from 28 days prior to enrollment until 30 days after the last dose of fedratinib must be reported on the eCRF. The type, dose route, start and end date of administration must be documented on the appropriate pages of the eCRF.

The details of the prior treatment with ruxolitinib and its outcomes will also be recorded in the subject's eCRF regardless of treatment discontinuation/procedure date.

Information regarding transfusion history (at least 84 days prior to and including the enrollment date), including pretransfusion hemoglobin (Hgb) levels, number of units transfused and dates of transfusions, will be collected and reported in the appropriate eCRF.

For information regarding other drugs that may interact with fedratinib and affect its metabolism, pharmacokinetics, or excretion, please also see the Investigator's Brochure.

8.1. Permitted Concomitant Medications and Procedures

Prophylaxis and/or treatment of gastrointestinal adverse events, specifically nausea, vomiting and diarrhea (eg, loperamide) is an essential part of management of potential fedratinib toxicity. (Refer to Section 7.3)

Subjects are required to take daily thiamine supplementation (Refer to Section 7.4)

Blood product support (RBCs and platelets transfusions) may be administered according to institutional standards.

Subjects may be administered supportive and palliative care (eg, pain control) as clinically indicated throughout the study.

Prior anticancer treatments should be recorded on the appropriate eCRF(s) regardless of treatment discontinuation/procedure date.

The details of the prior treatment and its outcomes will also be recorded in the subject's eCRF regardless of treatment discontinuation/procedure date.

For information regarding clinically relevant P450 inducers, inhibitors, substrates, and Transporter Substrates refer to Section 8.3.

8.2. Prohibited Concomitant Medications

The following concomitant medications are specifically excluded during the course of the study:

- Cytotoxic, chemotherapeutic, targeted or investigational agents/therapies
- Immunomodulatory drug therapy (eg, thalidomide)
- Immunosuppressive therapy

- Systemic corticosteroids >10 mg/day prednisone or equivalent
- Hydroxyurea
- Interferon-alpha
- Anagrelide
- JAK inhibitors other than fedratinib
- Aspirin at doses of > 150 mg daily
- Any investigational agent

For information regarding clinically relevant P450 inducers, inhibitors, substrates, and Transporter Substrates refer to Section [8.3](#).

If a subject requires treatment with any new medications that are specifically excluded, the subject may need to be discontinued from treatment. The Investigator should consult the Medical Monitor regarding any questions about whether a new medication or dosage of existing medication would require the subject to discontinue from the study.

8.3. Clinically Relevant Cytochrome P450 Inducers, Inhibitors, Substrates, and Transporter Substrates

Fedratinib is metabolized by multiple cytochrome P450 enzymes (CYPs) in vitro, with prominent contribution from CYP3A4 and with a lesser contribution from CYP2C19.

8.3.1. CYP3A4 Inducers and Inhibitors

Strong and moderate CYP3A4 inducers ([Appendix L](#)) that may decrease fedratinib plasma concentrations are not permitted while receiving fedratinib.

Strong CYP3A4 inhibitors ([Appendix L](#)) increase fedratinib plasma concentrations. In place of strong CYP3A4 inhibitors, alternative therapies that do not inhibit CYP3A4 need to be considered. If strong CYP3A4 inhibitors cannot be replaced, the strong CYP3A4 inhibitor needs to be used with caution and the fedratinib dose needs to be adjusted (refer to Section [7.2.2](#)).

8.3.2. Dual CYP2C19 and CYP3A4 Inhibitors

Dual inhibitors of CYP2C19 and CYP3A4 (eg, fluconazole, fluvoxamine) that may increase fedratinib plasma concentrations are not permitted while receiving fedratinib.

8.3.3. Sensitive Substrates: Effect of Fedratinib on Plasma Levels of Other Co-administered Drugs (Drugs Metabolized by CYP3A4, CYP2C19, and CYP2D6):

Co-administration of fedratinib with drugs that are CYP3A4 substrates (eg, midazolam), CYP2C19 substrates (eg, omeprazole), or CYP2D6 substrates (eg, metoprolol) increase the area under the plasma concentration curve from time zero to infinity (AUC_{inf}) of these drugs by 4-, 3-, and 2-fold, respectively, which may increase the risk of adverse reactions of these drugs.

Monitor for adverse reactions and adjust the dose of drugs that are CYP3A4, CYP2C19, or CYP2D6 substrates ([Appendix L](#)) as necessary when co-administering with fedratinib.

8.3.4. Transporters: Effect of Fedratinib on Plasma Levels of Other Co-administered Drugs (Drugs Transported by P-gp, BCRP, MATE1, MATE2-K, OATP1B1/1B3, and OCT1/2):

Fedratinib inhibits transporters P-gp, BCRP, MATE1, MATE2-K, OATP1B1/1B3, and OCT2, which may increase the concentration of drugs that are substrates of these transporters. Monitor for adverse reactions and adjust the dose of drugs that are substrates of these transporters ([Appendix L](#)) as necessary when coadministered with fedratinib.

A list of clinically relevant P450 inducers and inhibitors as well as substrates, and transporter substrates can be found in [Appendix L](#).

9. STATISTICAL CONSIDERATIONS

9.1. Overview

This is a multicenter, single-arm, open-label efficacy and safety study of fedratinib in subjects previously treated with ruxolitinib and with DIPSS-intermediate or high-risk primary myelofibrosis, post-polycythemia vera myelofibrosis, or post-essential thrombocythemia myelofibrosis.

The sections below provide an overview of the proposed statistical considerations and analyses. The final statistical analysis methods will be documented in detail in the statistical analysis plan (SAP).

General Considerations

Descriptive summary for continuous data will include the number of non-missing observations (n), mean, standard deviation, median, minimum and maximum. In addition, 25% percentile and 75% percentile may be provided if needed.

Categorical data will be summarized using counts (n) and percentages (%). The number of subjects with missing data may be displayed but will not be included in the denominator for the calculation of percentages unless otherwise specified.

Unless otherwise specified, baseline value is defined as the last value or measurement taken prior to the first dose in the study.

9.2. Study Population Definitions

Enrolled Population: this population includes all subjects enrolled into the study.

Safety population: this population will consist of all subjects who were administered at least one dose of fedratinib.

Efficacy evaluable population: this population includes subjects treated with fedratinib with evaluable spleen volume measurements based on MRI/CT scan at baseline and at least one post baseline response assessment by MRI/CT scan. This population will be used for analyses of spleen volume changes.

MFSAF population: For symptoms response (MFSAF version 4.0), fedratinib treated subjects with a Total Symptom Score (TSS) at baseline (eg, symptom score) > 0 and at least 1 post baseline TSS assessment will be included in the analysis.

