9.5. Subject Disposition

Subject disposition (analysis population allocation, entered, discontinued, along with primary reason for discontinuation) will be summarized using frequency and percentage for the study.

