9.6. Efficacy Analysis

Unless otherwise specified, analysis of spleen volume response will be performed on the efficacy evaluable population, myelofibrosis symptom response analyses will be performed on the MFSAF population and spleen size response analyses will be performed on the safety population.

9.6.1. Spleen Volume Response Rate (RR) by MRI/CT:

Response rate of reduction in spleen volume is defined as proportion of subjects who have a \geq 35% reduction in spleen volume at the end of Cycle 6 as compared to baseline. The response rate and 95% confidence interval will be provided. In addition, a descriptive summary of spleen volumes measurements and percentage change from baseline will be provided. Subjects with a missing MRI/CT spleen volume at the end of Cycle 6 including those who meet the criteria for progression of splenomegaly before the end of Cycle 6 will be considered non-responders.

A sensitivity analysis will be conducted for response rate of subjects who have a $\geq 25\%$ reduction in spleen volume at the end of Cycle 6 as compared to baseline.

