9.6.2. Spleen Response Rate by Palpation (RRP)

Spleen response rate by palpation is the proportion of subjects with a spleen response according to the IWG-MRT 2013 ([Appendix D](#)) at the end of Cycle 6 as compared to baseline. This will be

calculated for subjects that have an enlarged spleen (≥ 5 cm below LCM) at baseline. Subjects with a missing spleen size assessment at the end of Cycle 6 including those who meet the criteria for progression of splenomegaly before the end of Cycle 6 will be considered not to be responders. The response rate and 95% confidence interval will be provided.

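### Treated subjects with no post-baseline scan leave the primary response-rate denominator instead of counting as non-responders, and no named analysis puts them back

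*Combined protocol and SAP*

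**What the plan says.** Four parts of the combined protocol and SAP bear on this.

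- **Analysis set (9.2).** The set used for spleen volume is defined as follows: "this population includes subjects treated with fedratinib with evaluable spleen volume measurements based on MRI/CT scan at baseline and at least one post baseline". What must exist after baseline is an imaging assessment of response.
- **Use of the set (9.6).** By default, "analysis of spleen volume response will be performed on the efficacy evaluable population". This covers the primary endpoint.
- **Missing data (9.6.1).** "Subjects with a missing MRI/CT spleen volume at the end of Cycle 6" are counted as non-responders, including those with earlier splenomegaly progression.
- **Sensitivity (9.6.1).** The only such analysis named begins "A sensitivity analysis will be conducted for response rate of subjects who have a" and continues with a 25% reduction in place of 35%. It names no other population.

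An all-treated set already exists. The safety population is everyone given at least one dose, and for palpation "spleen size response analyses will be performed on the safety population". Section 9.5 will tabulate "analysis population allocation, entered, discontinued, along with primary reason for discontinuation", which does not include reasons for exclusion from the evaluable set. Section 1.3.2 allows for about 10 of 110 subjects being non-evaluable. Section 9.3 describes the same margin as 10% drop-out.

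**The concern.** The missing-scan rule in 9.6.1 looks like a full non-responder imputation, but it acts only on subjects already admitted to the set. A treated subject with no post-baseline scan is not admitted, so 9.6.1 never applies. Such a subject has no documented response. Removal leaves the numerator unchanged and shrinks the denominator, so the reported rate moves upward relative to all treated subjects.

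The subjects concerned are those who die, withdraw or are lost early, and they are likely to include treatment failures. In a single-arm study the response rate and its interval are the main result, and no control arm shares the bias. As planned, no all-treated rate or interval stands beside the primary one.

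**Working it through.** **Inputs.** Sections 9.3 and 1.3.2 give a 35% assumed response rate, 100 evaluable subjects, about 110 enrolled, and a two-sided 95% exact (Clopper-Pearson) interval whose lower bound should exceed 20%. The number treated but never scanned after baseline, *d*, is not given. I assume 110 treated, the *d* subjects non-responders, and *d* from 0 to 10. The upper end uses the plan's whole allowance for non-evaluable subjects of every kind, so it is a ceiling.

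**The plan's own figure.** The lower bound for x responders of n is the 0.025 quantile of Beta(x, n − x + 1). At n = 100 it is 19.5% for x = 28 and 20.4% for x = 29, so 29 responders are needed. P(X ≥ 29 | n = 100, p = 0.35) = 91.5%, which reproduces the stated power of about 90%. The sample size is not in question.

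**Effect on the rate.** If 35% of scanned subjects respond, the all-treated rate is 0.35 × (110 − d)/110.

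| d | All-treated rate | Difference from 35% (points) |
|---|---|---|
| 2 | 34.4% | 0.6 |
| 4 | 33.7% | 1.3 |
| 5 | 33.4% | 1.6 |
| 8 | 32.5% | 2.5 |
| 10 | 31.8% | 3.2 |

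**Effect relative to the 20% sizing figure.** The smallest count whose lower bound exceeds 20% is 31 for n = 106–110, 30 for n = 102–105 and 29 for n = 100–101. The last column takes a true all-treated rate of 20%, so the rate among scanned subjects is 22/(110 − d), and gives the probability of reaching the cut-off on the evaluable set.

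| d | Cut-off, evaluable set | Cut-off, 110 treated | Counts that differ | P(lower bound > 20%) |
|---|---|---|---|---|
| 0–4 | 31 | 31 | none | 2.4–2.5% |
| 5–8 | 30 | 31 | 30 | 3.9–4.0% |
| 9–10 | 29 | 31 | 29, 30 | 6.2% |

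For example, 30/105 has a lower bound of 20.2% and 30/102 has 20.8%, but 30/110 has 19.2%.

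**Design case.** With d = 10 and 35 responders, 35/100 = 35.0% (95% CI 25.7–45.2%) and 35/110 = 31.8% (23.3–41.4%). Both exclude 20%.

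**The case against.** The strongest reply is that the gap is narrow and the plan already limits it. Scans are due at the end of Cycle 3 and at End of Treatment. Table 3, footnote b sends subjects who stop before Cycle 4 to response assessment at the End of Treatment visit, and section 6.2.1 requires that visit whatever the reason for withdrawal. Exclusion 26 removes subjects expected to live less than 6 months. Most early stoppers will therefore be scanned and counted as failures. This stands, and it is why the effect is called small.

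The 20% figure belongs only to the sizing, where it is defined on evaluable subjects, and 9.6.1 states no success rule. The 3.9–6.2% probabilities are therefore not errors in the stated design. This also stands; they only show scale. If 35% of scanned subjects respond, the chance of landing on a count that differs is 3.2% at d = 5, 4.2% at d = 8 and 8.8% at d = 10.

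A reader could divide the responders by the safety population from the tables. That is true of the point estimate, but it leaves the interval and the reasons for exclusion unreported, and such an analysis would not be prespecified.

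Section 9.1 calls section 9 an overview and leaves final methods to the SAP. No more detailed text was available, so a further sensitivity analysis there cannot be ruled out. The analysis set, however, is fixed in 9.2 and 9.6.

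The palpation analysis does use all treated subjects, and "Subjects with a missing spleen size assessment at the end of Cycle 6" are likewise not responders there. But it is a secondary endpoint, limited to a baseline spleen of at least 5 cm, and cannot stand in for the primary one.

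Finally, a screening scan is required of everyone, so a missing baseline scan should be rare, and calling such a subject a non-responder could bias the rate downward. That is a reason to state the rule, since the question arises once the safety population is the denominator.

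**Conclusion.** The concern holds and should be fixed. Sections 9.2 and 9.6 together exclude treated subjects with no post-baseline scan from the primary rate, and no named analysis restores them. The direction is known for subjects with a baseline scan: the reported rate is at or above the all-treated rate.

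The size depends on an unknown *d*. It is 0.6 to 1.6 percentage points for 2 to 5 unscanned subjects and 3.2 points at the ceiling of 10, assuming 110 treated, 35% response among those scanned and no response among the rest. With four or fewer unscanned, no result changes sides of 20%. At the design case the conclusion is safe throughout. The main consequence is a somewhat high rate and interval, not a failed design. Confidence is high about the analysis set. That no all-treated analysis is planned rests on the text available.

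**What to change.** Keep the efficacy evaluable population as the primary analysis set, and make three additions.

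1. In 9.6.1, beside the 25% threshold analysis, prespecify a sensitivity analysis of the primary endpoint in the safety population, with treated subjects lacking a post-baseline scan counted as non-responders and the same exact 95% interval.
2. State how that analysis handles a missing or unevaluable baseline scan. Inclusion criterion 5 lets a subject qualify by palpation alone, so the case can arise.
3. In 9.5, report the number of treated subjects excluded from the efficacy evaluable population, with reasons.

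The cost is protocol or SAP wording and one extra table. No patients, visits or procedures are added, and the primary set and its power (91.5% at 100 evaluable) are unchanged. The downside is that a possibly slightly lower rate appears beside the primary one.

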9.6.3. Symptom Response Rate (SRR)

Symptom response rate (SRR) is defined as the proportion of subjects with $\geq 50\%$ reduction from baseline to the end of Cycle 6 in total symptom score (TSS) measured by MFSAF version 4.0. The SRR and 95% confidence interval will be provided. The TSS will be defined as the sum of each of the 7 symptom scores (Gwaltney, 2017). To allow indirect comparison with previous MF studies, a modified TSS (Mesa, 2013) will also be derived from the 6 symptoms considered (night sweats, pruritus, abdominal discomfort, early satiety, pain under ribs on left side, bone or muscle pain) and analysis of SRR will be also performed.

At each timepoint, the TSS (based on 7 symptoms) and the modified TSS will be calculated. Descriptive summary statistics (size, mean, standard deviation, median, range) will be provided for baseline scores, postbaseline scores and change from baseline for TSS, modified TSS and symptom scores.

Subjects without a baseline TSS > 0 will be considered non-evaluable (due to no place for symptom reduction) for the SRR analysis. Subjects with a missing TSS at the end of Cycle 6 or who had disease progression before the end of the Cycle 6 will be considered non-responders.

Details of the statistical analysis will be provided in a separate Health-related Quality of Life (HRQoL) SAP and will be reported under a separate cover.

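### The MFSAF population drops treated subjects with no TSS after baseline from the symptom response rate, although Section 9.6.3 points to counting them as non-responders; the effect is probably small and can only raise the rate relative to that count

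*Combined protocol and SAP*

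**What the plan says.** Three parts of the protocol's statistical section decide who is in the SRR denominator.

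- **Section 9.6** assigns the population: "myelofibrosis symptom response analyses will be performed on the MFSAF population".
- **Section 9.2** defines that population as fedratinib-treated subjects with a baseline TSS above 0, and adds that only those with "at least 1 post baseline TSS assessment will be included in the analysis".
- **Section 9.6.3** defines response as a reduction of at least 50%, measured as "reduction from baseline to the end of Cycle 6 in total symptom score (TSS) measured by MFSAF version 4.0". It gives its own rule on evaluability: "Subjects without a baseline TSS > 0 will be considered non-evaluable". Its missing-data rule names "Subjects with a missing TSS at the end of Cycle 6" and classes them as failures, along with anyone whose disease progressed by then.

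Section 9.1 sets a general default under which subjects with missing data "will not be included in the denominator for the calculation of percentages unless otherwise specified". For SRR, Section 9.6.3 does specify otherwise.

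Section 6.7.1 and Table 3 schedule the MFSAF at screening, on Day 1 of every cycle, at response assessments, at the End of Treatment (EOT) visit and at the 30-Day Follow-up. Section 9.6.3 leaves further detail to a separate HRQoL SAP, which is not among the documents.

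**The concern.** Take a treated subject with a positive baseline TSS and no TSS afterwards. That subject has no TSS at the end of Cycle 6. Section 9.6.3 read alone makes the subject an evaluable non-responder, because its only ground for non-evaluability is the baseline score. Section 9.2 takes the same subject out of the denominator. Two programmers could report different SRRs from the same data, each with text to cite.

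The exclusion also depends on what happens after dosing starts. Those removed would be subjects who die, withdraw consent or are lost early and complete no later form, and none of them can be a responder. The study has a single arm, so there is no control group with a matching exclusion. The SRR and its interval are the result for this endpoint, and Section 9.6.3 adds a modified 6-symptom score so that the rate can be set beside earlier myelofibrosis studies. The denominator matters for that use.

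**Working it through.** **The plan's own figures.** The documents give no planned SRR, power or sample size for this endpoint, so there is no SRR figure to reproduce. The approximately 90% power in Section 9.3 belongs to the primary spleen-volume endpoint. It does reproduce (29 of 100 responders needed for an exact 95% lower bound above 20%; exact power 91.5% at a true rate of 35%), but it has no bearing on SRR.

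**Who is removed.** Baseline is the last value before the first dose (Section 9.1), so the first routine post-baseline form is Cycle 2 Day 1. A subject who stops in Cycle 1 is still due a form at EOT (Section 6.2.1) and at the 30-Day Follow-up (Section 6.3.1). Any one of these keeps the subject in the population, as a non-responder if the Cycle 6 TSS is missing. Only a subject with none of them is removed.

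**Direction.** Let N be the treated subjects with baseline TSS above 0, x the responders, and k those with no later TSS. The k subjects cannot be among the x.

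- All counted: x / N
- Section 9.2 rule: x / (N − k)
- Difference: xk / [N(N − k)], which is never negative, and is zero only if k = 0 or x = 0.

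**Size.** Assumptions, none of them planning values for SRR:

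- N = 110: the planned enrolment (Section 9.3), as if all were treated with a baseline TSS above 0.
- x = 28: from 0.256 × 110 = 28.2. The 25.6% is the symptom response rate that Section 1.2 quotes for the earlier single-arm phase 2 study after ruxolitinib.
- k = 0 to 11: the upper end is 10% of 110, as if every planned drop-out completed no later form.

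| k | SRR | Shift (points) | Exact 95% CI |
|---|---|---|---|
| 0 | 28/110 = 25.5% | 0 | 17.6 to 34.6% |
| 1 | 28/109 = 25.7% | +0.2 | 17.8 to 34.9% |
| 3 | 28/107 = 26.2% | +0.7 | 18.1 to 35.6% |
| 5 | 28/105 = 26.7% | +1.2 | 18.5 to 36.2% |
| 11 | 28/99 = 28.3% | +2.8 | 19.7 to 38.2% |

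Check of the last row: 28 × 11 / (110 × 99) = 308 / 10,890 = 0.028.

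The shift grows with the rate. With 38 of 110 responders (34.5%), it is +0.3 points for k = 1 (38/109 = 34.9%) and +3.8 points for k = 11 (38/99 = 38.4%).

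**The case against.** The strongest reply is that the sections nest. Section 9.6 sends symptom response to the MFSAF population, Section 9.2 defines it, and the missing-data rule of Section 9.6.3 can be read as working inside it. The spleen-volume analysis has the same structure. On that reading there is no textual contradiction, and a reader who infers a flat conflict goes further than the documents. What stands is that Section 9.6.3 gives its own evaluability rule without mentioning post-baseline data. On the nested reading the exclusion and its direction are also unchanged.

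A reader might infer that early drop-outs in general leave the denominator. They do not. EOT and 30-day forms are due whatever the reason for stopping, and Section 6.7.1 allows other modes of administration in exceptional circumstances.

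A reader might also infer that the reported SRR is biased in the drug's favour with nothing to offset it. The documents do not support that. Section 9.6.3 counts every missing Cycle 6 TSS as failure, including that of a subject still on treatment who missed one form, and counts earlier progression as failure whatever the TSS. Both pull the rate down. The upward direction holds only against full non-responder counting; net bias against the true response rate is not established.

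Two further points stand. The 25.6% is a loose anchor: Section 1.2 gives no denominator for it, and it rests on a modified diary that the same section describes as covering 6 symptoms, whereas the main score here has 7 items. And the HRQoL SAP may already settle the denominator or plan a sensitivity analysis, but that cannot be checked. The population is defined in the protocol, so the wording should be settled there in any case.

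**Conclusion.** The point holds in a limited form. Sections 9.2 and 9.6.3 are at best ambiguous about treated subjects with a positive baseline TSS and no later TSS. Leaving them out can only raise the SRR relative to counting them as non-responders, and this direction is arithmetic that needs no assumption.

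The size does rest on assumptions. If 1 to 3 of an assumed 110 subjects are excluded, the shift is 0.2 to 0.7 points, against a 95% interval about 17 points wide. The 2.8-point shift requires the whole planned drop-out to miss every later form and is best read as an upper bound. SRR is secondary and is reported as a rate with a 95% interval. No test, threshold or sample size depends on it, so only the estimate and interval are affected. The change is worth making because it is cheap and removes an exclusion based on post-treatment events, not because a large distortion is expected.

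**What to change.** For SRR, on both the 7-item and the modified TSS:

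- Use all treated subjects with a baseline TSS above 0 as the denominator, and count a missing end-of-Cycle-6 TSS as non-response.
- Keep the requirement for a post-baseline TSS only for the change-from-baseline summaries.
- Report the number of subjects with no post-baseline TSS.
- Carry the same wording into the HRQoL SAP.

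The protocol already follows this pattern for palpation response. Section 9.6 uses the safety population, and Section 9.6.2 restricts it only by baseline spleen size and counts a missing Cycle 6 assessment as non-response.

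No new data are needed. The cost is an edit to Section 9.2, a sentence saying which set serves SRR and which serves the change summaries, and an SRR that may come out slightly lower.
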